2.6. Other Definitions

For FDA marketing authorization approval in the US all subjects will be included in the analysis.

The oseltamivir subset (OST subset) contains only those subjects with oseltamivir (OST) use as part of their SOC treatment. The first dose of OST may be given before the subject was randomized but should be started no later than the day of first study drug intake.

The complete analysis will be repeated restricted to the OST subset to support marketing authorization approval in EMA.

Analyses to support authorization approval in other regions or countries, will include all subjects (depending on the enrichment of the interim analysis) unless the Health Authority of the regions or country requests otherwise and may be specified in a separate analysis plan and may also be reported separately

3. INTERIM ANALYSIS AND DATA MONITORING COMMITTEE REVIEW

3.1. Interim Analyses

An interim analyses will be performed by an independent Statistical Support Group (SSG) and will be reviewed by the Independent Data Monitoring Committee (IDMC). Only the IDMC and the SSG will be unblinded to the data. The IDMC will provide recommendations to a Sponsor Committee.

An interim analysis will be implemented to assess lack of efficacy in the subgroup with time since onset of influenza symptoms between 72 and 96 hours.

- In case lack of efficacy is concluded for the subgroup with time since onset of influenza symptoms between 72 and 96 hours:
 - Enrollment in this subgroup will be stopped
 - Sample size re-estimation will be performed based on the subgroup with time since onset of influenza symptoms ≤ 72 hours and consequently, the sample size of this subgroup may be increased. The maximum number of subjects that may be enrolled in this subgroup will be approximately 900.
 - Futility will be assessed in the subgroup with time since onset of influenza symptoms ≤ 72 hours based on re-estimated sample size.
 - At the final analysis, hypotheses will be evaluated in the subgroup with time since onset of influenza symptoms ≤ 72 hours.
- In case no lack of efficacy is concluded for the subgroup with time since onset of influenza symptoms between 72 and 96 hours:
 - The subgroup with time since onset of influenza symptoms between 72 and 96 hours will be continued in the study.
 - Sample size re-estimation will be performed based on all subjects. The sample size may be increased. The maximum total number of subjects that may be enrolled in the study

will be approximately 900. The study population should consist of at least 75% of subjects with first administration of study drug ≤ 72 hours since onset of influenza symptoms.

- Futility will be assessed in all subjects based on re-estimated sample size.
- At the final analysis, hypotheses will be evaluated in all subjects.

Details on the statistical decision rules will be provided in the IDMC SAP. The interim analysis will be conducted at the end of the first influenza season when between 300 and 450 subjects have been enrolled or during the season when 450 subjects have been enrolled. Further details will be specified in the IDMC charter.

3.2. Independent Data Monitoring Committee

An IDMC will be established to monitor data on a regular basis. The committee will meet periodically to review interim data. After the review, the IDMC will make recommendations regarding the continuation of the study. The details will be provided in a separate IDMC charter.

The IDMC will consist of at least 3 members, including one medical expert in the relevant therapeutic area and at least one statistician knowledgeable about statistical methods for clinical studies and sequential analysis of study data. One of these individuals will chair the Committee. The IDMC responsibilities, authorities, and procedures will be documented in its charter.

4. SUBJECT INFORMATION

All general analyses will be done on the ITT-i Set and the Safety Set unless specified otherwise for a specific display.

4.1. Demographics and Baseline Characteristics

Demographics and baseline disease characteristics will also be done on the PP and ITT-ni sets.

Descriptive statistics or frequency tabulation will be provided for the following parameters.

- Demographic parameters:
 - Sex (Male, Female)
 - Race (White, Black or African American, Asian, American Indian or Alaska Native, Native Hawaiian or Other Pacific Islander, Multiple). The specification of the category ‘Multiple’ will only be listed. The ‘Not reported category’ will not be added for the denominator.
 - Ethnicity (Hispanic or Latino, Not Hispanic or Latino)
 - Country
 - Geographic region (Based on country according to UN classification of Geographic regions^[9]: Europe/Africa, Northern-America, Latin America and the Caribbean, Asia and Oceania)
 - Age (years and categories: 13-17 years [≥ 13 - < 18], 18-65 years [≥ 18 - ≤ 65], 66-85 years [> 65 - ≤ 85])
 - Age (years and categories: Adolescents (12-17 years) [≥ 12 - ≤ 17], Adults (18-64 years) [≥ 18 - ≤ 64], From 65 to 84 years [≥ 65 - ≤ 84], 85 years and over [≥ 85])
 - Weight at baseline (kg)
 - Height at baseline (cm)
 - BMI at baseline = Weight at baseline (kg) / (Height at baseline (m))² (rounded to 1 decimal. Although available in the raw data, BMI will be recalculated from last weight and height measurement before start of treatment)
 - Current Tobacco use: tobacco, cigarettes, cigars, patches/gum, pipes, E-cigarettes or equivalent, smokeless tobacco (Yes, No, Missing). Note that ‘No’ also includes ex-smokers.
 - Childbearing potential (only listed)

- Baseline disease characteristics:
 - Influenza A subtype category (A/H1N1, A/H3N2, No subtype)
 - Baseline influenza A viral load (\log_{10} vp/mL), assessed by qRT-PCR
 - Baseline influenza A viral titer (\log_{10} TCID₅₀/mL) assessed by viral culture

- qRT-PCR negativity at baseline
- Viral culture negativity at baseline
- Broad respiratory panel (show the reported pathogen)
- Return to daily activities at baseline
- Patient Global Impression of Severity of Influenza symptoms at baseline
- EQ-5D VAS at baseline
- EQ-5D Valuation index at baseline
- NEW2 Score at screening (4-5, ≥ 6), as randomized
- NEW2 Score at screening (4-5, ≥ 6), actual
- Hospital recovery scale category at baseline
- Fundamental hospital recovery scale category at baseline
- Respiration rate at baseline (breaths/min)
- Arterial oxygen saturation at baseline on room air (%)
- Arterial oxygen saturation at baseline overall (%)
- Supplemental oxygen at baseline (yes, no) (following supplemental oxygen types are considered: nasal cannula, venturi mask, simple face mask and nonrebreathing face mask with reservoir and one way valve)
- Mechanical ventilation use at baseline (yes, no)
- Temperature ($^{\circ}\text{C}$) at baseline
- Systolic blood pressure at baseline (mmHg)
- Heart rate at baseline (beats/min)
- Level of consciousness at baseline
- Time since onset of influenza symptoms as randomized (≤ 72 , >72 hours),
- Time since onset of influenza symptoms, actual time (hours) [the actual time will be calculated from start date and time of acute respiratory symptoms until datetime of first study drug intake, if the time is missing, the midpoint of the time interval as recorded per CRF will be used.]
- Time since onset of influenza symptoms, actual (≤ 72 , >72 hours)
- Time since onset of influenza symptoms, actual – 3 categories (≤ 48 , $>48 - 72\text{h}$, >72 hours)
- Type of SOC at baseline, as randomized (including or not including influenza antiviral treatment)
- Type of SOC at baseline, actual (including or not including influenza antiviral treatment), for the SOC including antiviral treatment the influenza antiviral will also be shown

- SOC including oseltamivir (yes, no)
- Chronic oxygen use (yes, no)
- Primary reason for hospitalization at baseline (prioritize influenza in case ≥ 2 reasons are selected, then adverse event and then medical history)
- Type of influenza A diagnostic assay (Rapid antigen-based diagnostic test, Rapid molecular diagnostic test)
- In ICU at baseline (yes, no)
- Baseline resistance
- Any baseline polymorphism

4.2. Disposition Information

Summaries will be provided for the following disposition information:

- Number of subjects screened, screening failures, randomized, randomized and not treated, randomized and/or treated, randomized and treated, randomized and no confirmed Influenza A, ITT-i set, ITT-ni set, per protocol set, and safety set. The planned treatment arm will be shown, except for the randomized and/or treated and safety sets where the actual treatment will be shown. The number (%) of subjects impacted by the COVID-19 pandemic will be presented for the ITT-i, ITT-ni, per protocol and safety analysis sets.
- Number of subjects who completed/discontinued treatment and/or the trial, with the reasons of discontinuation. The number of subjects that discontinued due to an AE that is related to COVID-19 and that discontinued due to another reason related to COVID -19 will be added.
- Kaplan-Meier curves of the time to completion or discontinuation (in days) of the treatment/trial per treatment group, overall and separately for subjects with/ without treatment extension. Note at the final analysis all subjects will have the event of completion or discontinuation and no subjects will be censored.
- Number of subjects with a visit at each scheduled analysis timepoint by phase and the missing visits and visits different from planned due to COVID-19 per phase.
- Number of subjects enrolled per month, quarter, season and year.

4.3. Treatment Compliance

Treatment compliance for pimodivir/placebo is calculated as the actual number of doses taken, as a percentage of the planned number of doses. The actual number of doses taken will be derived from the drug accountability information (DA domain) as the amount of drug dispensed minus the returned amount (in case both amounts are known, otherwise treatment compliance will be missing)

To differentiate between the compliance during the planned treatment subperiod and the planned treatment extension subperiod, the date of dispensing the tablets will be compared with the treatment extension start date (DS Domain). If the drug is dispensed before the treatment extension

start date it will be used for the compliance of the treatment subperiod. If the drug is dispensed on or after the treatment extension start date the amount will be used for the compliance of the treatment extension subperiod.

For placebo or pimodivir the actual number of doses needs to be divided by 2 as the study uses 300 mg tablets. For subjects without treatment extension the planned number of study drug is 20 tablets of placebo or pimodivir hence the planned number of doses per study drug equals 10 doses. For subjects with treatment extension the planned dose is doubled. Note that the planned number of doses is irrespective of whether the subject discontinued during the treatment phase.

Dosing compliance will be summarized descriptively in the treatment phase and per subperiod and by discontinuing the trial during the treatment period (Yes, No).

4.4. Extent of Exposure

The extent of exposure (hours) is defined as datetime of last study drug intake – datetime of first study drug intake + 12 hours. Note: treatment interruptions will not be taken into account.

Extent of exposure will be summarized descriptively in the treatment phase, overall and by treatment subperiod.

A listing will be made to present the exposure to study drug for subjects impacted by COVID-19 (based on reason ‘Other’ containing ‘COVID’).

4.5. Protocol Deviations

The number and percentage of subjects with major protocol deviations will be tabulated overall and per coded major protocol deviation.

A listing will be made of all major protocol deviations for the subjects in the safety set.

Additionally, a listing of major and separately a listing for minor protocol deviations related to COVID-19 will be made.

Additionally, for subjects in the ITT-i set, the number and percentage of subjects with a reason for exclusion from the per protocol set will be tabulated overall and for each reason for exclusion.(see Section [2.2.2.2](#)).

A listing will also be made of all reasons for exclusion from the per protocol set for subjects in the ITT-i set.

4.6. Prior and Concomitant Medications

Medications reported from 7 days before first dose of study drug and up to last contact date will be summarized by preferred term using the World Health Organization-Drug Dictionary for the ITT-i Set and the Safety Set as frequency tables in 2 parts:

1. Prior medication: medication that started before the first dose of study drug, regardless of when dosing of the medication ended
2. Concomitant medication: medication received at or after the first dose of study drug, medication that was received before initial dosing and continued after initial dosing of study drug, or medication with missing stop date.

(Medication that started before the first dose of study drug and continued after the first dose of study drug will be summarized as prior medication and separately as concomitant medication.)

A frequency tabulation of concomitant medication will be shown by ATC class level up to level 3. Frequency tabulations will be made for concomitant antibiotics, type of SOC, corticosteroids, and medication administered to treat COVID-19 infection by ATC class and by hospitalization status. Additionally, tabulations will be made of concomitant corticosteroids and antibiotics administered because of adverse events reported as influenza complications.

The ATC level 2 code J01 will be used to identify concomitant antibiotics.

The ATC level 2 code H02 and the ATC level 4 codes M01BA, R03BA, and R03AK will be used for identifying corticosteroids. Separate frequency tabulations will be made for antipyretic medication and oxygen supplementation. The ATC level 4 codes N02BA and N02BE and the generic medication names paracetamol, ibuprofen, and acetylsalicylic acid will be used to identify antipyretic medications. The table showing oxygen supplementation will be tabulated per analysis visit, phase and treatment subperiod. If a prior/concomitant therapy record misses components of its start and/or stop dates (time and/or day and/or month and/or year), the following actions will be taken:

1. In case of partial start or stop datetimes, the concomitant therapy records will be allocated to prior and/or concomitant using the available partial information, without imputations.
2. In case of a completely missing start date, the prior and/or concomitant therapy will be considered as having started before the trial.
3. In case of a completely missing end date, the prior and/or concomitant therapy will be considered as ongoing at the end of the trial.

4.7. Medical history

The influenza vaccination status will be tabulated by:

- Vaccinated in previous season, not in current season
- Vaccinated in current season, not in previous season
- Vaccinated in previous and current season.
- Not vaccinated in previous and current season

The use of antiviral influenza medication prior to study drug initiation will be tabulated separately.

Influenza history will be listed, including information on first acute respiratory symptoms, influenza vaccination status, chronic oxygen use and previous antiviral influenza therapy. Pre-treatment influenza complications will also be listed.

Other medical history will be tabulated by subcategory and/or will be listed.

5. EFFICACY

Descriptive statistics will be used for all efficacy endpoints and will be tabulated by treatment arm and stratification factors (NEWS2 at screening, baseline SOC and time since onset of symptoms). For the analyses restricted to subjects who received OST as part of their SOC, type of baseline SOC will not be included as a stratification factor or model parameter.

5.1. Analysis Specifications

5.1.1. Level of Significance

The population used for the evaluation at the final analysis will depend on the outcome scenario of the interim analysis: i.e.; scenario 1: continue with the full study population or scenario 2: continue only with the subjects with an onset of symptoms less than 72 hours before first study drug intake. Tables/graphs/listings will account for the selected scenario.

As a confirmatory strategy, to account for multiplicity in the statistical evaluation of the most important efficacy endpoints, in either scenario, a combination of hierarchical testing and the Bonferroni-Holm testing procedure will be applied to control for the overall Type I error rate at the 5% level. The following endpoints are included in the confirmatory strategy:

1. Hospital recovery scale at Day 6, ie, primary endpoint
2. Incidence in post-baseline complications
3. Time to hospital discharge
4. Time from ICU admission to ICU discharge
5. Time to return to daily activities
6. Time from start of mechanical ventilation to end of mechanical ventilation
7. Rate of re-hospitalization

First, the primary endpoint will be tested for superiority of pimodivir in combination with SOC over placebo in combination with SOC at the 2-sided 5% significance level.

The confirmatory test procedure follows the Serial Gate Keeping strategy as outlined in Section 7 of the FDA's draft guidance on Multiple Endpoints to control the overall type I error at the 5% 2-sided level. The primary and six most important secondary endpoints (listed above) will be tested in the hierarchical order per the 5 steps outlined below. All alphas and p-values specified are 2-sided.

Step 1: Test the primary hypothesis ("Hospital recovery scale at Day 6")

- If the p-value is $\leq 5\%$, continue to Step 2.
- If the p-value is $> 5\%$, stop testing, and no claim will be made.

Step 2: Test first set of 2 secondary endpoints (“Incidence in post-baseline complications” and “Time from start of study drug to hospital discharge”). The Bonferroni-Holm procedure will be applied to control the type I error within Step 2.

- If the smallest of the 2 p-values is $\leq 2.5\%$ and the largest of the 2 p-values is $\leq 5\%$, continue to Step 3.
- If the p-value for “Incidence in post-baseline complications” is $\leq 2.5\%$ but the p-value for “Time from start of study drug to hospital discharge” is $> 5\%$, stop further testing of the secondary endpoints, and make a claim on “Hospital recovery scale at Day 6” and “Incidence in post-baseline complications”.
- If the p-value for “Time from start of study drug to hospital discharge” is $\leq 2.5\%$ but the p-value for “Incidence in post-baseline complications” is $> 5\%$, stop further testing of the secondary endpoints, and make a claim on “Hospital recovery scale at Day 6” and “Time from start of study drug to hospital discharge”.
- If the smallest of the 2 p-values is $> 2.5\%$, stop further testing of the secondary endpoints, and make a claim on “Hospital recovery scale at Day 6” only.

Step 3: Test second set of 2 secondary endpoints (“Time from ICU admission to ICU discharge” and “Time to return to daily activities”). The Bonferroni-Holm procedure will be applied within Step 3.

- If the smallest of the 2 p-values is $\leq 2.5\%$ and the largest of the 2 p-values is $\leq 5\%$, continue to Step 4.
- If the p-value for “Time from ICU admission to ICU discharge” is $\leq 2.5\%$ but the p-value for “Time to return to daily activities” is $> 5\%$, stop further testing of the secondary endpoints, and make a claim on “Hospital recovery scale at Day 6”, “Incidence in post-baseline complications”, “Time from start of study drug to hospital discharge” and “Time from ICU admission to ICU discharge”.
- If the p-value for “Time to return to daily activities” is $\leq 2.5\%$ but the p-value for “Time from ICU admission to ICU discharge” is $> 5\%$, stop further testing of the secondary endpoints, and make a claim on “Hospital recovery scale at Day 6”, “Incidence in post-baseline complications”, “Time from start of study drug to hospital discharge” and “Time to return to daily activities”.
- If the smallest of the 2 p-values is $> 2.5\%$, stop further testing of the secondary endpoints, and make a claim on “Hospital recovery scale at Day 6”, “Incidence in post-baseline complications” and “Time from start of study drug to hospital discharge”.

Step 4: Test the fifth secondary endpoint (“Time from start to end of mechanical ventilation”)

- If the p-value is $\leq 5\%$, continue to Step 6.
- If the p-value is $> 5\%$, stop further testing of the secondary endpoints, and make a claim on “Hospital recovery scale at Day 6”, “Incidence in post-baseline complications”, “Time from start of study drug to hospital discharge”, “Time from ICU admission to ICU discharge”, and “Time to return to daily activities”.

Step 5: Test the sixth secondary endpoint (“Rate of re-hospitalization”)

- If the p-value is $\leq 5\%$, make a claim on “Hospital recovery scale at Day 6”, “Incidence in post-baseline complications”, “Time from start of study drug to hospital discharge”, “Time

from ICU admission to ICU discharge”, “Time to return to daily activities”, “Time from start to end of mechanical ventilation”, and “Rate of re-hospitalization”.

- If the p-value is >5%, make a claim on “Hospital recovery scale at Day 6”, “Incidence in post-baseline complications”, “Time from start of study drug to hospital discharge”, “Time from ICU admission to ICU discharge”, “Time to return to daily activities”, and “Time from start to end of mechanical ventilation”.

For the primary endpoint, the results from the proportional odds model will be used in the hypothesis testing. If the proportional odds assumption would not hold on the treatment effect, the p-value from the van Elteren test will be used. For the secondary endpoints time from start of study drug to hospital discharge, time from ICU admission to ICU discharge, time to return to daily activities, and time from start to end of mechanical ventilation, the results of the Gehan-Wilcoxon test will be used in the hypothesis testing. For incidence in post-baseline complications and rate of re-hospitalization the results of the logistic regression will be used. For all these evaluations p-value combination tests will be used, as described below.

The final analysis on the ITT-i set (to support FDA marketing approval) and the final analysis on the OST subset (to support marketing authorization approval in EMA) will be performed independently, using a 5% two-sided significance level for each.

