11.3. Sample Size Determination

The study will enroll 600 subjects between the ages of 13 and 85 years, inclusive. Subjects will be randomized 1:1 to one of the treatment arms.

The sample size is based on the primary endpoint of the hospital recovery scale at Day 6. Based on the proportional odds model and assuming a benefit of approximately 38% reduction of the common odds ratio, a total sample size of 600 subjects (randomized 1:1) is required to obtain a power of 90%.¹⁹ Inclusion of stratification factors would provide some improvement on the derived power.

In the sample size calculation, it is assumed that the distribution of subjects treated with placebo in combination with SOC treatment will be as follows on Day 6:

- Not hospitalized: 30%
- Non-ICU hospitalization, not requiring supplemental oxygen: 30%
- Non-ICU hospitalization, requiring supplemental oxygen: 25%
- Admitted to the ICU, not requiring invasive mechanical ventilation: 5%
- Requiring invasive mechanical ventilation: 5%
- Death: 5%

This sample size is robust to mild to moderate changes in this distribution.

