For the primary endpoint, the results from the proportional odds model will be used in the hypothesis testing. For the secondary endpoints time from start of study drug to hospital discharge, time from ICU admission to ICU discharge, time to return to daily activities, and time from start to end of mechanical ventilation, the results of the Gehan-Wilcoxon test will be used in the hypothesis testing. For incidence in post-baseline complications and rate of re-hospitalization the results of the logistic regression will be used.

Primary Endpoint

The primary efficacy analysis will be based on the ITT-i analysis set and consists of the analysis of the hospital recovery scale outcome on Day 6.

A proportional odds model will be used to analyze the hospital recovery scale, including at a minimum treatment and the stratification factors (baseline NEWS2, type of baseline SOC, and time since onset of influenza symptoms).

Model assumptions will be assessed by the score test for parallel slopes. In addition, each of 5 dichotomizations of the hospital recovery scale, ie,

- Not hospitalized, vs worse (ie, hospitalized)
- Non-ICU hospitalized without supplemental oxygen (or better), vs worse
- Non-ICU hospitalized with supplemental oxygen (or better), vs worse
- In the ICU without invasive mechanical ventilation (or better), vs worse
- Invasive mechanical ventilation (or better), vs worse (ie, died)

will be analyzed using a logistic regression model, including at a minimum treatment, hospital recovery scale category at baseline, and strata. The hospital recovery scale will also be analyzed using the Van Elteren test with strata defined by the stratification factors.

In case of more than 10% missing data on Day 6, multiple imputation will be employed as sensitivity analyses, under the missing-at-random (MAR) assumption and missing-not-at-random (NMAR) assumption. For the NMAR assumption, imputation under the MAR assumption will be applied, but with a structural shift in hospital recovery scale category of the imputed values, to introduce non-ignorable missing patterns:

- To reflect missingness patterns as a result of study discontinuation due to a dissatisfying treatment effect or safety issues in the placebo treatment group, the following shifts will be applied in the placebo treatment group only:
 - 1 category down, eg, from ‘1. Not hospitalized’ to ‘2. Non-ICU hospitalization, not requiring supplemental oxygen’

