5.2.3. Analysis Methods

A proportional odds model will be used as primary model to analyze the hospital recovery scale on Day 6, modeling the common odds ratio of improvement on the ordinal scale of active treatment versus placebo. The model will include treatment, hospital recovery scale category at baseline and the stratification factors (NEWS2 category at screening, type of baseline SOC, and time since onset of influenza symptoms). In a first step equal slopes (i.e. proportional odds) for the treatment effect only and unequal slopes for the other covariates, will be modeled. If this model does not fit a full

proportional odds model will be applied, i.e. implying proportional odds for all covariates in the model. The common odds ratio from the final model will be considered as the estimate of the treatment effect. The actual values of the stratification factors will be used for all models, not as randomized. The proportional odds model will be defined in such a way that a common odds ratio smaller than 1 indicates larger improvement in the pimodivir treatment group.

Graphical displays and tabulations will be provided showing the proportion of subjects per hospital recovery scale category and day. Also, shift tabulations will be provided of the baseline hospital recovery scale category versus the post-baseline hospital recovery scale category, per day.

The proportional odds assumption will be assessed by testing for parallel slopes for the treatment effect only.

In addition, each of 5 dichotomizations of the hospital recovery scale, ie,

- Not hospitalized, vs worse (ie, hospitalized)
- Non-ICU hospitalized without supplemental oxygen (or better), vs worse
- Non-ICU hospitalized with supplemental oxygen (or better), vs worse
- In the ICU without invasive mechanical ventilation (or better), vs worse
- Invasive mechanical ventilation (or better), vs worse (ie, died)

will be analyzed using a logistic regression model, including treatment, hospital recovery scale category at baseline and stratification factors.

The hospital recovery scale will also be analyzed using the Van Elteren test with strata defined by the stratification factors^[3, 6].

A table will be created showing the number (%) missing HRS values at day 6 overall and by reason: study discontinuation: due to COVID-19 and not due to COVID-19, discharged against medical advice prior to day 5 and subjects that have no confirmed influenza A.

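### The SAP's fallback confirmatory test for the primary endpoint (van Elteren) drops baseline hospital recovery scale, a covariate that its own proportional odds model carries

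*SAP*

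**What the plan says.** Protocol 11.4 fixes the test: "For the primary endpoint, the results from the proportional odds model will be used in the hypothesis testing". On the model it says: "A proportional odds model will be used to analyze the hospital recovery scale, including at a minimum treatment and the stratification factors". It checks parallel slopes with a score test but attaches no consequence to the result, and it lists van Elteren as an additional analysis. Baseline recovery scale (HRS) is named there only for the five dichotomised logistic regressions.

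The SAP differs in two ways.

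- Section 5.2.3 puts baseline HRS category into the primary proportional odds model, beside treatment and the three stratification factors.
- Section 5.1.1 adds a switch: "If the proportional odds assumption would not hold on the treatment effect, the p-value from the van Elteren test will be used". Section 5.2.2 repeats it, calling van Elteren a sensitivity analysis while passing its p-value to the formal test.

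For the van Elteren test, section 5.2.3 says: "The hospital recovery scale will also be analyzed using the Van Elteren test with strata defined by the stratification factors". Baseline HRS is not among the strata.

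Protocol 11.3 sizes the trial "assuming a benefit of approximately 38% reduction of the common odds ratio"; on that basis "a total sample size of 600 subjects (randomized 1:1) is required to obtain a power of 90" per cent.

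**The concern.** If the check on treatment slopes fails, the confirmatory p-value moves from a test adjusted for baseline HRS to one that is not. The outcome is the same scale some five days later, and inclusion criterion 5 admits patients from ward-level hypoxia to invasive ventilation, so baseline category may well be prognostic. Protocol 3.2 itself ranks baseline severity among the strongest predictors of outcome.

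The NEWS2 stratum (4-5 versus 6 or more) is a coarse substitute. Under the substitution rule in SAP 7.6.1 a ventilated subject scores at least 3 + 2 + 3 = 8. A ward patient on oxygen with SpO2 91% and respiratory rate 22 scores 3 + 2 + 2 = 7. Both fall in the same stratum.

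The stake is the whole confirmatory sequence: under SAP 5.1.1, missing the primary endpoint stops all later testing.

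**Working it through.** **1. The plan's own figure.** Inputs from Protocol 11.3: odds ratio 0.62, 1:1 allocation, placebo distribution 30/30/25/5/5/5%. Level from SAP 5.1.1: 5% two-sided. Whitehead's formula is N = 12(z₀.₉₇₅ + z₀.₉₀)² / [(ln OR)²(1 − Σp̄³)].

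- Active arm at OR 0.62: 40.9/29.9/19.4/3.4/3.3/3.2%. Averaging the arms gives Σp̄³ = 0.0825.
- N = 12 × 10.507 / (0.2285 × 0.9175) = 601.4. Power at 600 is 89.9%.

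The stated figure reproduces. It uses no covariates.

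**2. Simulation set-up.** N = 600, with randomisation balanced within the eight strata and the placebo distribution as above. Assumed, because the documents are silent:

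- baseline HRS categories 3/4/5 at 80/12/8%, with a check at 95/3/2%;
- odds ratios for categories 4 and 5 versus 3: none, moderate (2.7, 7.4), strong (4.5, 20), very strong (20, 148);
- stratum prevalences 60/85/75%;
- the slope check as a 4-df likelihood-ratio test at 5%.

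There were 4000 replicates per scenario, and 1500 for the 95/3/2% check. This simulation did not include the two-stage combination test.

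**3. Power (%) at marginal OR 0.62, proportional odds true**

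| Baseline HRS effect | SAP model | van Elteren as written | van Elteren + HRS strata | Switch procedure overall |
|---|---|---|---|---|
| None | 90.4 | 90.3 | 89.2 | 90.4 |
| Moderate | 93.4 | 90.8 | 92.2 | 93.2 |
| Strong | 95.1 | 89.2 | 94.2 | 94.7 |
| Very strong | 98.8 | 89.6 | 98.2 | 97.5 |

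**4. Power (%) among replicates where the check fired, SAP model / van Elteren as written.** Each pattern lists the treatment odds ratios at the five cut points, from discharge to death.

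| Pattern | None | Moderate | Strong | Very strong | Strong, 95/3/2% |
|---|---|---|---|---|---|
| .62, .62, .70, 1, 1 | 85.5/85.0 | 88.4/86.1 | 91.6/86.0 | 95.5/88.0 | 87.3/86.1 |
| .55, .70, .85, 1, 1 | 83.0/83.7 | 88.0/84.9 | 89.9/85.3 | 95.2/86.6 | 87.1/86.4 |
| .85, .60, .45, .45, .45 | 73.4/72.6 | 77.8/70.9 | 83.7/70.6 | 94.1/70.5 | 78.5/73.8 |
| .55, .65, 1, 1.5, 1.5 | 87.3/87.0 | 90.6/88.1 | 93.7/87.3 | 97.5/87.5 | 90.2/87.4 |

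The differences are within 1 point (none), 2.3 to 6.9 (moderate), 4.6 to 13.1 (strong), 7.5 to 23.6 (very strong), and 0.7 to 4.7 when 95% share one baseline category. The Monte Carlo standard error of each entry is about 1 point, and about 1.5 in the last column.

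**5. Source of the loss.** In every scenario van Elteren as written and a proportional odds model without baseline HRS differ by 1 point or less. The loss therefore comes from dropping the covariate, not from changing the type of test.

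**6. Type I error.** The two-sided rate of the switch procedure was 5.0 to 5.8%. The SAP model gave the same range in the same runs (standard error about 0.35 points, 0.56 in the smaller run).

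**7. The remedy.** Across steps 3 and 4, full HRS strata cost 0.7 to 1.8 points when HRS was not prognostic (for example 74.0% down to 72.2%, all replicates of the third pattern). A further simulation, including a 400 + 200 two-stage combination, pooled baseline HRS into ward versus ICU/ventilated. That recovered about 1.5 to 5 points when HRS was prognostic, cost about 1 point when it was not, and left type I error at 4.5 to 5%.

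**The case against.** Much of the opposing case stands.

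- **The protocol's minimum model does not name baseline HRS.** Against that model the switch costs 1 point or less. The loss exists only relative to the SAP's own model.
- **A rank-test fallback specified in advance is a defensible choice,** and the SAP fixes its direction. A reader might infer that the switch inflates the type I error. Step 6 does not show this. Inflation would need a free choice of the better p-value, which the SAP does not allow.
- **A reader might infer that the switch leaves the trial underpowered.** At the planned marginal effect the van Elteren test keeps 89 to 91%, which is what the covariate-free sample size promised.
- **The entry criterion concentrates subjects in category 3,** which limits what adjustment can gain. Hence the smaller range at 95/3/2%.
- **Full HRS stratification is sparse within a stage.** In a separate run with an assumed 150 to 300 subjects per stage and four HRS levels, 24 to 28 strata were occupied and 7 to 9 of them held one arm only, discarding 4 to 9% of subjects. This counts against unpooled strata; pooling answers it.

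A reader might also infer that the switch must be made separately for the pre- and post-interim p-values of SAP 5.1.2. The documents do not say either way.

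**Conclusion.** The point holds as a cheap improvement in efficiency and consistency. The SAP replaces the protocol's confirmatory p-value under a stated condition, and the replacement omits a covariate that the SAP's primary model includes. When the switch fires, the loss against that model is about 0 points if baseline HRS is not prognostic, 2 to 7 if moderate, 5 to 13 if strong, up to about 24 if very strong, and about 1 to 5 if nearly all subjects share one baseline category.

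These sizes rest on assumed baseline spread, prognostic strength, non-proportional patterns and a 5% trigger. When proportional odds holds, the switch seldom fires and the overall cost is 0 to 1.3 points (step 3, first column minus last). The unstated trigger level is missing detail and would not justify a change by itself.

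**What to change.** Either of two changes to the SAP, before unblinding:

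- **Add baseline HRS to the van Elteren strata** wherever that p-value can be the formal one, pooled for example as ward versus ICU/ventilated. Strata rise from 8 to 16 in the full population. They rise from 4 to 8 where the time factor drops out (the 0-72 hour analyses) or SOC type does (the oseltamivir subset).
- **Or keep the proportional odds model with baseline HRS as the sole confirmatory test,** in line with the protocol, and report van Elteren as a sensitivity analysis. The common odds ratio is then an average if slopes differ; the planned dichotomised regressions already show the pattern.

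If the switch stays, also state the level of the slope test, which of the two models in section 5.2.3 carries it, and whether it is decided once or for each stage p-value. Bring section 5.2.2's sensitivity label and the protocol into line.

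The cost is wording. The downside of the first option is more and smaller strata, and about 1 to 2 points of power if baseline HRS is not prognostic.
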